Effects of neural mobilization augmented by traditional physical therapy on pain, functional disability and H-reflex in patients after lumbar laminectomy: a randomized controlled trial

March 19, 2019

Objective: The purpose of the study was to determine whether the addition of neural mobilization to a standard postoperative physical therapy program could improve the outcome of patients after lumbar laminectomy.

Design: Randomized controlled trial with blinded evaluators.

Setting: The study was conducted in outpatient physical therapy clinic.

There are fewer studies examining physical therapy programs for post-operative rehabilitation after lumbar surgery. The aim of the current study was to establish whether the addition of neural mobilization to a standard postoperative physical therapy program is valuable for patients who had undergone lumbar decompressive laminectomy.

Methods

Participants

Sixty patients of both sexes, aged from 35-50 years who underwent lumbar laminectomy of one or two levels shared in the study. They were recruited from the orthopedic surgery and neurosurgery departments, Cairo University hospitals. The purpose and procedures were explained to each patient before participation. A signed informed consent was taken from all patients who accept participation in the study. Approval of the Research Ethical Committee of the Faculty of Physical Therapy, Cairo University was obtained (P.T.REC/012/002241). This study followed the principles of Helsinki Declaration.

Exclusion criteria

- Patients who had arthritis in the joints of the lower limbs (which would limit walking).
- Patients who had tumors, fractures or infections of the spine.
- Patients who had diabetes mellitus.
- Patients who had polyneuropathy
- Patients who had evidence of spinal cord compression.
- Patients who had previous spinal surgery, spinal stability problems (e.g. spondilo-listhesis, spondilolysis).
- Patients who had sensory loss.

Participants were randomly assigned through computer-generated random numbers into two groups. The study group consisted of 30 patients (15 females and 15 males). Patients in this group received neural mobilization in addition to a selected physical therapy program. The control group consisted of 30 patients (12 females and 18 males) and treated with the same selected physical

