7) Alternately raising two opposite limbs from quadruped position at the same time: this exercise was started at the 9th week post-surgery. From quadruped position with maintaining the head and back straight, the patient was instructed to raise both one upper limb with the opposite lower limb simultaneously till horizontal level and hold this position for 5 seconds then return them. Then, the patient was asked to repeat this with the other two limbs. This exercise was repeat 2 times.

Each the previous sets of exercises was done 5 sets with 30 seconds rest in between sets. During exercises, patients were instructed to keep normal respiration and avoid holding of breathing. The selected exercises was done for a total of 30 to 45 minutes according to the types of exercises given to the patient.

Effects of neural mobilization augmented by traditional physical therapy on pain, functional disability and H-reflex in patients after lumbar laminectomy: a randomized controlled trial

Statistical Analysis

March 19, 2019

Sample size

The sample size was calculated prior to the study. Calculation was performed using G*POWER statistical software [F tests- MANOVA: Repeated measures, within-between interaction, $\alpha=0.05$, $\beta=0.2$, effect size = 0.37] and revealed that the required sample was N=60.

Statistical analysis

All statistical analysis was out using the Statistical Package for Social Studies (SPSS) version 25 for windows (IBM SPSS, Chicago, IL, USA).

Descriptive statistics and t-test were conducted for comparison of subject characteristics between both groups.

Chi- squared test was used for comparison of sex distribution. Shapiro–Wilk test was used to explore the normality of data. Levene’s test was used to check the homogeneity between groups.

Mixed MANOVA was conducted to compare within and between groups effects on visual analogue scale (VAS), Oswestry Disability Index (ODI) and H-reflex latency. Post-hoc tests using the Bonferroni correction were performed for subsequent multiple comparison. The level of significance for all statistical tests was set at $p < 0.05$.

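### The trial is sized on the group-by-time interaction, but the analysis text designates no treatment contrast as the deciding test, and the two effects it names are poor bases for a claim of benefit

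*Combined protocol and SAP*

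**What the plan says.** The objective is comparative: "whether the addition of neural mobilization to a standard postoperative physical therapy program could improve the outcome of patients after lumbar laminectomy". There are two arms of 30 (Participants) and two assessments, one before and one after the six weeks of treatment (Outcome measures).

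Under Sample size, the calculation is described as "F tests- MANOVA: Repeated measures, within-between interaction", with alpha 0.05, beta 0.2 and "effect size = 0.37"; it "revealed that the required sample was N=60".

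Under Statistical analysis, the model is introduced with "Mixed MANOVA was conducted to compare within and between groups effects on visual analogue scale (VAS", ODI and H-reflex latency. The follow-up is: "Post-hoc tests using the Bonferroni correction were performed for subsequent multiple comparison". That paragraph does not mention the interaction, does not say which comparisons the post-hoc tests make, and does not say which result decides whether the added treatment works.

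**The concern.** With two arms measured before and after treatment, the effect of adding neural mobilization is the difference between arms in change or, equivalently in aim, the difference at the end given the baseline. The sample size paragraph reflects this and the analysis paragraph does not. Its two named effects answer other questions or answer this one weakly.

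- The within-group effect asks whether patients changed between the two assessments. Both arms receive active therapy from four weeks after surgery, so both may improve whether or not the added treatment does anything.
- The between-groups main effect averages the two assessments. The first precedes treatment, so randomization makes its expected difference zero and the average carries half of the post-treatment difference.
- Unlisted post-hoc tests leave room for separate pre/post tests in each arm, and so for a claim of benefit because one arm reached significance and the other did not.

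At stake are a missed effect, if the main effect decides, and an unsupported claim, if within-arm tests decide.

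**Working it through.** **Inputs from the documents.** Two groups of 30, two assessments, alpha 0.05, power 0.80, effect size 0.37, N=60. **Assumptions.** The effect size is read as f for the interaction. SDs are equal in both arms and at both times (σ). The pre/post correlation ρ is not given, so 0, 0.3, 0.5 and 0.7 are shown.

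**Step 1: reproduce N=60.** With two groups and two times the interaction test is F with 1 and N − 2 = 58 degrees of freedom and noncentrality λ = N·f² = 60 × 0.37² = 60 × 0.1369 = 8.21. Power is 0.805, and 60 is the smallest N that reaches 0.80. The stated figure is right for this test on one outcome. For two equal groups the standardised difference is 2f = 0.74, so the trial is sized for a difference in change of 0.74 SD of change.

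**Step 2: the same effect under other tests.** The SD of change is σ√(2(1 − ρ)), so the post-treatment difference is δ = 0.74·σ√(2(1 − ρ)).

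- Main effect: it estimates δ/2, and the SD of a patient's two-assessment average is σ√((1 + ρ)/2). The standardised difference is 0.74·√((1 − ρ)/(1 + ρ)).
- Post-treatment comparison without adjustment: δ/σ = 0.74·√(2(1 − ρ)).
- Post-treatment comparison adjusted for baseline: residual SD σ√(1 − ρ²), giving 0.74·√(2/(1 + ρ)).

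Power is from the two-sided noncentral t with 30 per arm and noncentrality d·√(30/2), on 58 degrees of freedom (57 with baseline adjustment), one outcome at 0.05. Each cell gives d, then power.

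| ρ (assumed) | Interaction | Main effect | Post-treatment, unadjusted | Post-treatment, baseline-adjusted |
|---|---|---|---|---|
| 0 | 0.74; 0.805 | 0.740; 0.80 | 1.047; 0.98 | 1.047; 0.98 |
| 0.3 | 0.74; 0.805 | 0.543; 0.54 | 0.876; 0.92 | 0.918; 0.94 |
| 0.5 | 0.74; 0.805 | 0.427; 0.37 | 0.740; 0.80 | 0.854; 0.90 |
| 0.7 | 0.74; 0.805 | 0.311; 0.22 | 0.573; 0.59 | 0.803; 0.86 |

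The main effect would need 60, 110, 174 and 328 patients for 80% power at these four correlations.

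**Step 3: the within-group effect.** In 4,000 simulated trials per correlation (0.3, 0.5, 0.7) with no treatment effect and an assumed 1-SD improvement in both arms, the pre/post test in one arm rejected in 99% to 100%. It carries no information about the added treatment.

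**Step 4: one arm significant, the other not.** With no true difference between arms, and each arm's pre/post test having power p, the pattern of study arm significant and control arm not has probability p(1 − p) per outcome:

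- p = 0.50: 0.50 × 0.50 = 25%
- p = 0.80: 0.80 × 0.20 = 16%
- p = 0.90: 0.90 × 0.10 = 9%
- p = 0.975: 0.975 × 0.025 = 2.4%, or about 2.5%

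The reference is 2.5%, the chance of a false finding in the favourable direction from a two-sided 5% test. The last line corresponds to both arms improving by 0.74 SD of change with 30 patients each.

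**The case against.** A reader might infer that the named tests do not measure the treatment effect and lack the stated power. The documents do not support that, for four reasons.

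1. A mixed MANOVA with group and time contains their interaction, and the sample size paragraph in the same short section names it. The phrase about effects within and between groups may be shorthand for the mixed design. Nothing says the interaction is left out.
2. Under randomization the between-groups main effect is a valid, though diluted, test of treatment. A post-hoc comparison of the arms at post-treatment would measure the effect directly, with power of at least 0.80 for correlations up to about 0.5 before any Bonferroni adjustment.
3. The loss of power arises only if the main effect decides, which the plan does not say, and its size depends on a correlation that the plan does not give. At zero correlation there is no loss.
4. The plan nowhere says that discordant within-arm results would count as benefit. The error rate of that reading depends on unknown per-arm power and falls to the nominal level or below when both arms improve strongly.

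All four stand, and they limit the point to what is unspecified. They do not remove it: the plan does not say that the interaction or the post-treatment comparison is the deciding test, and it leaves the weaker routes open.

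**Conclusion.** The point holds as a gap in specification. The contrast that was powered is not designated as the treatment test, and neither is any other. N=60 is correct for the interaction on one outcome (power 0.805), so the sample size is not in error on this point.

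The size of the problem is conditional. If the main effect were used to decide, power for the planned effect would be 0.80, 0.54, 0.37 and 0.22 at correlations of 0, 0.3, 0.5 and 0.7. If discordant within-arm tests were used, the false-claim rate per outcome would be about 25%, 9% or 2.5% at per-arm power of 50%, 90% or 97.5%; that reading is invalid whatever the rate. These figures assume equal SDs, no systematic baseline difference, and 0.37 read as f for the interaction.

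A better test is available at no cost. Adjusting the post-treatment value for the baseline already collected gives power of about 0.98, 0.94, 0.90 and 0.86 at the same correlations, above the interaction throughout. All these powers are for one outcome at 0.05. With an assumed Bonferroni split over the three outcomes, the interaction test on each has power 0.66.

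**What to change.** Amend the Statistical analysis paragraph to say:

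- The treatment test for each outcome (VAS, ODI, H-reflex latency) is the between-group difference at post-treatment adjusted for that outcome's baseline value. At minimum, name the group-by-time interaction, which is the test the sample size was computed for.
- The estimate is reported with a 95% confidence interval.
- Post-hoc tests are limited to that between-group contrast, and the number of comparisons entering the Bonferroni correction is stated.
- The between-groups main effect and the within-group pre/post tests are descriptive and cannot support a claim of benefit.

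The cost is a few sentences. No new data are needed, and N=60 does not change for a single outcome.

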therapy program only. The treatment started after four weeks postoperative.²¹ All patients received their treatment three sessions/week for six successive weeks.

Outcome measures

All measurements were conducted by examiners who were blinded to the patient's group. All patients were evaluated for; 1) Leg pain intensity: It was evaluated through visual analogue scale (VAS). VAS is a 10-cm line with a "0" at the left end for "no pain" and 10 at the right end for "worst possible pain", each patient was asked to indicate on the line where his pain is in relation to the two extremes by circling the number. 2) Functional ability: It was evaluated by Oswestery disability index (ODI). The ODI is a valid and reliable tool for assessment of functional ability.

3) Nerve root compression: It was assessed through assessment of latency of H-reflex of S₁. The participant was in prone-lying position. The active recording electrode was located on the soleus between the two heads of the gastrocnemius, while reference recording electrode was located on the Achilles tendon. The stimulation was applied at the midline in the popliteal fossa on the tibial nerve. The active stimulating electrode was closer to the spine. Stimulation was performed manually every 2 seconds (sec) with a stimulus duration of 0.5 or 1.0 msec. The intensity of stimulation was increased gradually and H-reflex & M-wave were watched. The latency is measured automatically by the device from the beginning of stimulation to the beginning of the initial deflection of the H-reflex. Assessment was conducted after surgery by four weeks before starting the study (initial evaluation) and repeated after treatment (post-treatment evaluation).

[figure not shown]

Figure 1: Flow chart of participants

Physical therapy intervention

Patients in the study group received neural mobilization in the form of straight leg raising (SLR) and dorsiflexion with two-ended slider that were designed to mobilize the neural tissues. Both groups received a selected physical therapy treatment which included TENS and dynamic back and abdominal exercises.

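### The single MANOVA on three outcomes needs six values per patient, so an unrecordable H-reflex at either visit would also remove that patient's valid pain and disability scores

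*Combined protocol and SAP*

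**What the plan says.** The SAP, under Statistical analysis, names one main analysis for all outcomes, a mixed MANOVA for group and time "effects on visual analogue scale (VAS), Oswestry Disability Index (ODI) and H-reflex latency". Bonferroni post-hoc tests follow. The software is "Statistical Package for Social Studies (SPSS) version 25 for windows".

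The protocol, under Outcome measures, sets two assessments, one "before starting the study (initial evaluation) and repeated after treatment (post-treatment evaluation"). It defines the electrophysiological outcome this way: "The latency is measured automatically by the device from the beginning of stimulation to the beginning of the initial deflection of the H-reflex".

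Under Sample size, the calculation "revealed that the required sample was N=60". Under Participants, 60 patients are described, 30 in each group.

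The documents do not say what is entered when no H-reflex can be elicited, how incomplete records are handled, which patients form the analysis set, or whether the post-hoc tests use the joint data set or all data available for each outcome. A recordable H-reflex is not an entry condition.

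**The concern.** A mixed MANOVA on three outcomes at two times treats each patient as one vector of six numbers. If one is absent, the standard procedure leaves the whole patient out. This is a property of the method and of the repeated-measures procedure in the named software; the plan does not state it.

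H-reflex latency is the outcome most exposed. VAS and ODI can be scored for any patient who attends, but latency runs to the onset of a deflection and does not exist if there is no deflection. The protocol uses this measure to assess nerve root compression, so an absent reflex may be related to the condition under study, although the documents do not say so.

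At stake are the pain and disability results. Under the joint model they would be estimated only in patients with a recordable reflex at both visits, although their own data are complete. This goes beyond the lack of a missing-data rule: joining the outcomes carries a gap in one into the other two.

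**Working it through.** **Inputs.** From the SAP: three outcomes, alpha 0.05, beta 0.2, effect size f = 0.37, required N = 60, and the design "F tests- MANOVA: Repeated measures, within-between interaction". From the protocol: two assessments, two groups of 30. The numbers of groups and measurements used in the power calculation are not stated; two and two are inferred from the design. The documents give no missing-data rate, so every rate below is an assumption.

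**Step 1: values needed per patient.** The joint model needs 3 × 2 = 6. One outcome analysed alone needs 2.

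**Step 2: reproduce the plan's figure.** For the group-by-time interaction with two groups and two measurements of one outcome, df1 = 1, df2 = N − 2 and noncentrality λ = f² × N. At N = 60, λ = 0.1369 × 60 = 8.21 with df2 = 58, and power is 0.805. N = 60 is the smallest total that reaches 0.80 on this formula; N = 59 gives 0.798. The stated sample size is therefore reproduced, as a one-outcome calculation at unadjusted alpha 0.05 with all 60 patients complete.

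**Step 3: only the H-reflex is missing.** A share h of patients lacks a recordable reflex at one or both visits, and nothing else is missing. The joint model keeps 60 × (1 − h); VAS and ODI analysed separately keep 60 each.

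| Assumed h | Joint model N | Power | VAS or ODI alone, N | Power |
|---|---|---|---|---|
| 5% | 57 | 0.78 | 60 | 0.805 |
| 10% | 54 | 0.76 | 60 | 0.805 |
| 20% | 48 | 0.71 | 60 | 0.805 |

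**Step 4: any value may be missing.** Each value is missing independently with probability m. The joint model keeps 60 × (1 − m)^6 and one outcome alone keeps 60 × (1 − m)^2. The effect of joining the outcomes is the gap between these two, not the fall from 60.

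| Assumed m | Joint model N | Power | One outcome alone, N | Power |
|---|---|---|---|---|
| 2% | 60 × 0.886 ≈ 53 | 0.75 | 60 × 0.960 ≈ 58 | 0.79 |
| 5% | 60 × 0.735 ≈ 44 | 0.67 | 60 × 0.9025 ≈ 54 | 0.76 |

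Joining the outcomes costs about 5 patients at 2% and about 10 at 5%. If values go missing together, as when a patient misses the second visit, the gap is smaller. If all three outcomes are missing together it is zero.

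**Step 5: when the reflex is absent.** Absence at the initial evaluation is known before treatment. Dropping those patients lowers N and narrows the population that the pain and disability results describe, but does not by itself bias the randomised comparison. Absence only after treatment arises after randomisation and may be affected by treatment, so dropping those patients can bias the comparison as well as reduce N.

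**The case against.** The strongest reply is that the loss is hypothetical. The documents report no missing value and no unrecordable reflex; both groups are described as 30, and the participant flow chart is not available in the text. Patients with diabetes, polyneuropathy or sensory loss are excluded and age is limited to 35–50, so an absent reflex should be less common than in an unselected group. The Bonferroni post-hoc tests might also be run per outcome on all available data. All of this stands: it makes the point conditional and favours the lower assumed rates. It does not remove the point, because none of these criteria requires a recordable reflex and the plan does not say that the post-hoc tests leave the joint data set.

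A second reply is that the power figures do not belong to pain or disability. This also stands. The SAP ties the effect size of 0.37 to no named outcome, and 0.805 takes no account of the Bonferroni step. The figures show relative loss on the plan's own terms, not the power for VAS or ODI.

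A third reply is that a sentence on incomplete data would suffice. Such a sentence is needed, but while the main analysis requires six values, a patient with no reflex has no latency to enter. Separate models are what free the VAS and ODI data.

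**Conclusion.** The point holds as a conditional weakness of the stated method. If an H-reflex is unrecordable at either visit, the joint model discards valid pain and disability data, and with 60 enrolled against 60 required there is no margin. For assumed rates of 5% to 20%, it keeps 57 to 48 patients (power 0.78 to 0.71) where separate analyses of VAS and ODI would keep 60 (0.805). At low rates the loss of power is modest.

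This rests on standard complete-case handling, on the inferred two-by-two power calculation, and on missing-data rates that the documents do not supply.

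A reader might infer more, and the documents do not support it:

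- That patients were in fact dropped. No missing value is reported.
- That the joint model is responsible for the whole fall from 60 to 53 or 44 under independent missingness. Separate analyses would also lose patients, keeping 58 or 54.
- That every such deletion biases the treatment comparison. Only absence arising after treatment raises that concern.
- That a reflex returning after treatment should count as improvement. The protocol defines the outcome as latency, so this would be a new endpoint.
- That the stated sample size is wrong. It reproduces on its own inputs.

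**What to change.** Make the main analysis one baseline-adjusted model (ANCOVA) for each of VAS, ODI and H-reflex latency, using every randomised patient with data on that outcome, in the group assigned. Apply the Bonferroni correction across the three outcomes, keep the mixed MANOVA as supportive, and report the number analysed for each outcome by group.

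Record whether the H-reflex was present or absent at each visit and report this descriptively by group beside the latency results, not as a fourth tested endpoint. The latency analysis will still cover only patients with a recordable reflex; the description lets the reader judge how selected they are.

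The cost is SAP wording and slightly more analysis, with no extra patients or visits. The omnibus test ceases to be the main analysis. The correction should also be stated openly: at alpha 0.05 / 3 = 0.0167, the formula in the working gives power of 0.66 at N = 60, before any gain from baseline adjustment. The plan already intends a Bonferroni step, so this is not wholly a new cost, but 0.805 should not be quoted for the corrected tests.

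### If the Bonferroni correction covers two or more post-hoc comparisons, Holm step-down over the same set would keep the familywise error and could detect more: an inexpensive efficiency gain, not an error

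*Combined protocol and SAP*

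**What the plan says.** The SAP, under Statistical analysis, plans one multivariate model for three outcomes: "Mixed MANOVA was conducted to compare within and between groups effects on visual analogue scale (VAS), Oswestry Disability Index (ODI) and H-reflex latency". The follow-up is given in one sentence: "Post-hoc tests using the Bonferroni correction were performed for subsequent multiple comparison". All tests use a 0.05 level. The text does not call this a familywise rate and does not state sidedness.

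The SAP does not say which post-hoc comparisons form the corrected set, how many there are, or whether the correction runs across VAS, ODI and H-reflex latency or only within each outcome. It mentions neither a step-down procedure nor simultaneous confidence intervals.

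The Sample size paragraph uses the G*Power option "MANOVA: Repeated measures, within-between interaction" with alpha 0.05, beta 0.2 and effect size 0.37, and "revealed that the required sample was N=60". The alpha is not divided over outcomes. The protocol has two groups of 30 and two assessments, before and after treatment.

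**The concern.** Single-step Bonferroni tests each of m p-values at alpha/m. Holm orders the p-values and tests the smallest at alpha/m, the next at alpha/(m−1) and so on, stopping at the first failure. It gives the same familywise protection with thresholds that are never stricter.

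The plan names three outcomes and no primary among them, so results on the second and third matter. N=60 only just reaches 80% power for a single test at 0.05. If the correction spans outcomes, single-step Bonferroni makes it more likely that a real effect on a second or third outcome is reported as non-significant, with no gain in error control.

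**Working it through.** **1. The plan's own figure.** Inputs from the Sample size paragraph: alpha 0.05, power 0.80, effect size 0.37 (read as G*Power's f(V)). From the protocol: 2 groups, 2 assessments. The interaction test is F with 1 and N−2 degrees of freedom and noncentrality λ = N × f².

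- N = 60: λ = 60 × 0.37² = 60 × 0.1369 = 8.21; power 80.5%.
- N = 59: power 79.8%.

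So 60 is the smallest adequate N, and the stated figure is reproduced. With two equal groups, f = 0.37 corresponds to d = 2 × 0.37 = 0.74 SD of the change score.

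**2. Holm against Bonferroni on the same set.**

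- *Rejections.* Since alpha/m ≤ alpha/(m−j+1) at every step j, each p-value that passes Bonferroni also passes Holm.
- *Error.* With m₀ true nulls, the first true null in the ordering is at step m−m₀+1 or earlier, so its threshold is at most alpha/m₀. The chance that any of m₀ true-null p-values falls at or below alpha/m₀ is at most alpha, whatever the correlation.
- *m = 1.* The methods coincide; power is 80.5% under both.

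**3. Size for an assumed set of three.** Assumptions, because the documents give none of these: m = 3 (one between-group comparison of change per outcome), two-sided tests, 0.74 SD for each real effect, 30 per arm, correlation 0, 0.3 or 0.6. Bonferroni tests all three at 0.05/3 = 0.0167. Holm uses 0.0167, 0.025 and 0.05. The noncentral F at 0.0167 gives 65.6% power per outcome under Bonferroni. Results from 200,000 simulated trials per scenario, as Bonferroni / Holm, for the real effects:

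| Real effects | Correlation | Power per outcome | At least one found | All real effects found |
|---|---|---|---|---|
| 3 | 0 | 65.6% / 75.2% | 95.9% / 95.9% | 28.2% / 50.1% |
| 3 | 0.3 | 65.5% / 74.3% | 91.4% / 91.4% | 35.6% / 55.5% |
| 3 | 0.6 | 65.5% / 73.4% | 85.6% / 85.6% | 43.2% / 61.2% |
| 2 | 0 | 65.6% / 69.5% | 88.1% / 88.2% | 43.1% / 50.9% |
| 2 | 0.6 | 65.5% / 68.8% | 79.5% / 79.5% | 51.5% / 58.0% |
| 1 | 0 | 65.6% / 65.8% | as per outcome | as per outcome |
| 1 | 0.6 | 65.5% / 65.6% | as per outcome | as per outcome |

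Holm failed to reject something Bonferroni rejected in 0 cases. With all three effects null, both methods had the same familywise error, 4.3-5.0%. With one or two real effects, Holm's was at most 4.4%.

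**4. Other set sizes.** For m = 6 with all effects real and correlation 0.3, power per comparison is 55.7% under Bonferroni and 67.3% under Holm.

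**The case against.** The strongest objection is that no loss has been shown for this plan. With two groups and two assessments, each simple contrast within one outcome (groups at one time, or times in one group) is a single comparison. If the correction works at that level, m = 1 and nothing is lost. This stands. A reader might infer that the plan certainly gives up power on all three outcomes; the SAP does not define the set, so that cannot be concluded.

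Second, a reader might think that the change can never hurt. That is true only over the same set. If the plan now corrects within each outcome (m = 1, power 80.5%), a three-outcome Holm family would lower power per outcome to about 73-75% with all three effects real, and to about 66% with one. If the set was meant to include pre/post contrasts within groups, naming only the between-group comparisons would leave those uncorrected. This also stands and shapes the fix.

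Third, Bonferroni offers something in return: simple simultaneous confidence intervals that match its tests. It is therefore too strong to say that the power is lost for nothing. The plan mentions no such intervals, however, so as written it does not use that advantage.

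Fourth, the case with all three effects real is the most favourable one. The SAP gives one effect size for one interaction test; it neither claims 0.74 SD for every outcome nor requires success on all three. This is fair, and the smaller gains belong beside the large one.

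Finally, the text is in the past tense and the protocol already reports the sex split of each group. The documents do not say whether outcomes had been analysed. Moving to a rule that rejects more after seeing results would be hard to defend, so timing matters.

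**Conclusion.** The point holds as a conditional efficiency improvement. For any corrected set of two or more comparisons, Holm is at least as powerful as Bonferroni at the same familywise error, with no assumption about correlation. That part does not depend on the simulation.

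The size does. Under the assumed set of three, the gain in power per outcome is 8-10 points if all three effects are real, 3-4 points if two are, and at most 0.2 points if one is. The chance of at least one finding changes by less than 0.1 point when two or three effects are real, because the first rejection uses the same threshold under both methods. For a single comparison the gain is zero.

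A reader might infer that the Bonferroni choice is a mistake or that it undermines N=60. Neither follows: Bonferroni is valid, and the sample size rests on the interaction test at undivided alpha 0.05, which this change does not touch.

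**What to change.** In the Statistical analysis section:

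1. State which comparisons are corrected together, for example the three between-group comparisons of VAS, ODI and H-reflex latency if the correction is meant to run across outcomes. This should record what the Bonferroni correction was meant to cover, not create a new family.
2. Replace the Bonferroni correction with the Holm step-down (sequentially rejective Bonferroni) correction over that same set, at a familywise two-sided 5%.
3. Report Holm-adjusted p-values. With the p-values in ascending order, the i-th adjusted value is the largest of (m−j+1) × p(j) over j ≤ i, capped at 1.
4. Make the change before outcome data are analysed. If they have already been analysed, keep Bonferroni as the stated method and say which comparisons it covered.

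The cost is a sentence or two in the SAP and a short calculation from the unadjusted p-values. It needs no extra patients or data. The drawback is that Holm has no simple matching simultaneous confidence intervals; if the sponsor wants those, keeping Bonferroni is a reasonable choice, provided the set is stated.
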